## **Eligibility Criteria**

### **Inclusion Criteria:**

The inclusions include both men and women over the age of 18 years old. Participants are unilateral trans-tibial amputees with a minimum of a 4" residual limb. This length of amputation was chosen to provide for adequate surface area for the electrodes. The participants must be a minimum of one year postoperative to insure proper healing of the limb has occurred. The participants must have chronic limb pain and have had no prior experience in using TENS or FES. Participants must also demonstrate the ability to voluntary elicit a muscle contraction.

### **Exclusion Criteria:**

The exclusion criteria include having a cardiac condition, such as hypertension, congestive heart failure, etc. The exclusions will be subjects who have a pacemaker and have impaired sensation measured by a monofilament test (unable to feel a minimum of 7/10 areas tested). The use of FES may interfere with a pacemaker and is not suggested for people who have a pacemaker. People with insensate skin and or neuropathy may lead to inappropriate threshold tolerance to the FES. Also, participants with a BMI greater than 42 kg/m^2 will be excluded as the FES does not work effectively with excessive adipose tissue.

## **Statistical Plan**

Descriptive statistics will be computed and variables will be assessed for normality. Nonparametric tests will be performed in the event the data are not normal. An unpaired t-test or chi-square test depending on the type of variable will be used to compare the subject demographic variables (e.g. age, level of amputation, gender, etc.) between groups. A mixed model repeated measures ANOVA will be used to compare the outcome measures between groups and overtime. Compliance with the FES (e.g. average number of hours of use per week) will be entered as a covariate. We will also use correlation statistics (Pearson or Spearman) to examine the relationship between amount of FES used and changes in the dependent variables. Should significant main and interaction effect differences be found ( $p < 0.05$ ), post-hoc analyses will be used to examine the differences in variables across the groups and time points. If the data fail to be normally distributed the Friedman test will be run.

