Most studies on FES have shown positive results when combining FES with activity (e.g. knee flexion/extension exercises, cycling etc.) (9). It is difficult to exercise a muscle that has been amputated and is partially intact. FES conditions the muscle similar to exercise. Our clinical experience has found improvements in knee function, socket fit, and reductions in pain with wearing FES alone. With this study, one of the main functional outcomes that we are investigating is knee extension. We plan to place the FES electrodes on the medial and lateral quadriceps muscles in hope to show positive changes in muscle strength and volume. The gastroc/ soleus and tibialis anterior muscles have been amputated and have a secondary insertion point, therefore they are difficult to strengthen by exercising. We would like to investigate the effects of the FES on these two muscles in hopes to decrease atrophy or increase muscle volume. Should we demonstrate that FES alone helps improve the outcome measures in this study; it could potentially be a highly practical, easy to use, cost effective treatment that can be done at home.

**Objective:** To determine if at-home FES use without prosthetic wear results in benefits to persons with unilateral, trans-tibial amputations (TTA) who are at least two years status post their amputation surgery.

Hypothesis 1: FES will increase knee extension strength in the residual limb

Hypothesis 2: FES will increase volume of the residual limb

Hypothesis 3: FES will decrease chronic and phantom pain of the residual limb

Hypothesis 4: In comparison to the control group, FES training will show greater increases in velocity, step length, and percentage in stance time on the amputated limb after training when compared to baseline as measured using the GaitRite System.

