## Study Design and Methods

Subjects will be recruited and randomized into two groups using a random block method at the end of the baseline visit. One group will receive the FES intervention and the other group will continue with their activities of daily living. The study consists of a baseline visit and four follow up visits at 4 weeks, 8 weeks, 12 weeks and one final visit three months from the 12 week visit or from the discontinuation of the FES. Outcome measures will be taken for both groups during these visits. Each visit is expected to take no more than two hours.

Following informed consent, it will be verified and documented that participants meet the inclusion/exclusion criteria. Most of the inclusion/exclusion criteria are self report, with the exception of the monofilament evaluation and the evaluation of voluntary muscle contraction. An investigator will administer the tests. For the sensory testing the participant will be asked to close their eyes and inform the investigator when they sense the pressure of the monofilament on their LE. In order to continue with the study procedures, the participant must be able to feel a minimum of 7 of the 10 areas tested. Participants will also be evaluated to determine if a voluntary muscle contraction is present. To do this the FES electrode pads will be placed on the participant and the investigator must be able to observe a muscle contraction in order to proceed. Any participants who do not meet the inclusion/exclusion criteria for the study will be withdrawn.

The following procedures and outcome measures will be obtained from a blinded (second) assessor at the baseline visit.

1. Residual knee extension strength will be tested using a standardized Biodex protocol and a custom attachment (System 3, Biodex Medical Systems, NY). The participant will practice first on the biodex machine with their intact limb.

2. The residual limb volume will be measured with the use of a hand held three-dimensional motion-tracking laser scanner system. Reflective markers will be placed on a sock over the residual limb located at the tibial tubercle, fibular head, and anterior distal tibia. Circumferential measurements of the residual limb will be taken with a tape measure. Longitudinal measurements of the residual limb will be taken with a straight ruler. Using a standard scale, participant's height and weight will be recorded.

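### Normality of the variables, not of the model residuals, decides whether an outcome keeps the between-group mixed model or goes to a Friedman test that has no group factor

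*Combined protocol and SAP*

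**What the plan says.** All of this stands in the Statistical Plan section unless noted.

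- The section opens with "Descriptive statistics will be computed and variables will be assessed for normality" and then "Nonparametric tests will be performed in the event the data are not normal".
- The outcome analysis is "A mixed model repeated measures ANOVA will be used to compare the outcome measures between groups and overtime". Effects are judged at 0.05, with post-hoc comparisons after significant results.
- The section closes with the outcome-specific rule: "If the data fail to be normally distributed the Friedman test will be run".
- Under Study Design and Methods, "Subjects will be recruited and randomized into two groups using a random block method at the end of the baseline visit", and "The study consists of a baseline visit and four follow up visits at 4 weeks, 8 weeks, 12 weeks and one final visit". That is two arms and five time points.
- Hypothesis 4, at the end of the Background section, is explicitly comparative: "In comparison to the control group, FES training will show greater increases in velocity, step length, and percentage in stance time".

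The plan does not name a normality test, a threshold or a graphical criterion. It does not say whether the check is made per outcome, per visit, per arm or on all values together. It does not say whether Friedman replaces or supplements the mixed model, though replacement is the natural reading. It states no sample size.

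**The concern.** A mixed model for repeated measures assumes normal residuals and normal person effects. It does not assume that the outcome is normal when arms and visits are put together. If FES works, values pooled over arms are a mixture of two distributions. Values stacked over visits repeat the same people and are not an independent sample. A check on the variables can therefore fail when the model is sound.

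The consequence lies in where a failed outcome goes. The mixed model is the only planned analysis that compares the outcome measures between arms. The Friedman test ranks each person's values over time. It has no group factor and takes no covariate. An outcome sent there loses the randomised comparison, for a reason that need have nothing to do with whether the model was valid. Because the check is left open, the analyst would also settle its form after seeing the data.

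**Working it through.** The plan gives no figure to reproduce: no sample size, power, SD or dropout.

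**Inputs from the documents.** Two arms; five visits, hence up to 2 × 5 = 10 arm-by-visit cells per outcome; 0.05 for the effect tests.

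**Assumptions, not in the documents.** Shapiro-Wilk at 5%; 10-30 people per arm; multivariate normal data with equal correlation between visits; the effect sizes shown below.

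**Step 1: ceiling by arithmetic.** With k independent 5% tests on normal data, the chance of at least one failure is 1 − 0.95^k.

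- k = 1: 5.0%
- k = 5: 1 − 0.95^5 = 22.6%
- k = 10: 1 − 0.95^10 = 40.1%

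Positive correlation between visits pulls the last two down somewhat.

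**Step 2: simulation, exactly normal data, no treatment effect, visit correlation 0.6-0.8.**

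| Form of the check | Normal outcomes diverted |
|---|---|
| One test, one visit, arms pooled | about 4-6% |
| Any of 5 visits, arms pooled | about 18-23% |
| Any of 10 arm-by-visit cells | about 35-40% |
| All values stacked as one sample | about 12-36%, rising with correlation |
| One test on residuals (arm-by-visit and person means removed) | about 4-5% |

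Over a wider correlation range of 0.5-0.9, the three multi-check rows become 15-23%, 30-41% and 9-55%.

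**Step 3: with a treatment effect at all follow-up visits, correlation 0.7, 15 or 30 per arm.**

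| Effect | Any of 5 visits | Stacked | Residuals |
|---|---|---|---|
| 0.8 SD | 22% | 19-21% | 4-5% |
| 1.5 SD | 17-19% | 25-33% | 5% |
| 2.5 SD | 28-46% | 74-92% | 5% |

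At 15 per arm and 2.5 SD, separate simulations of the stacked check gave 74% and 82%. At 0.8 SD the treatment effect adds almost nothing; the mixture problem becomes large only with very large effects.

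**Step 4: what diversion does (15 per arm, correlation 0.7, 5% level).** Friedman on all participants is set against a two-sample t-test on mean change from baseline.

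| True change at follow-up | Friedman rejects | Group comparison rejects |
|---|---|---|
| None in either arm | 4% | 5% |
| +0.5 SD in both arms | 89% | 5% |
| −0.5 SD in one arm, +0.5 SD in the other | 2-3% | 99% |

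The second row has no FES-control difference, and Friedman nearly always rejects. The third has a difference of 1 SD, and Friedman almost never does. Running Friedman within each arm would still give no test between arms.

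**The case against.** **Frequency.** A reader might infer that normal outcomes will often be diverted. The documents do not support that as a fact. One 5% test per outcome on one visit's data diverts about 1 normal outcome in 20, hardly different from a residual check. The higher rates need repeated checks or stacking, and the assessment could equally be made by plots or skewness. Nor does every outcome have five visits: the Prosthetics Evaluation Questionnaire is collected only at baseline, 12 weeks and the final visit. This stands, so the rates are conditional. The multi-check forms are still realistic, because strength, limb volume and pain are measured at all five visits and nothing in the plan rules those forms out.

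**Error rate.** A reader might also infer that any data-driven switch spoils the 5% level, whatever the fallback. That is not shown. With the strictest check (any of ten cells), normal data, no effect, and a switch between a t-test and a Mann-Whitney test on week-12 change, the overall type I error was 4.2-5.0%, against 4.4-5.2% for the t-test alone. The harm shown here comes from the check leading to Friedman, not from the check by itself.

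**Scope.** The two opening sentences of the section also serve the demographic comparisons, and the plan offers Pearson or Spearman correlations. Inspecting the variables is ordinary practice there. This stands too, and it limits the change needed.

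**Conclusion.** The point holds in this form: for the outcome measures, the plan ties the choice of analysis to normality of the variables or data, does not specify the check, and sends a failing outcome to a test that cannot compare FES with control. That much rests on the text, taking Friedman as a replacement for the mixed model.

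The frequency is conditional. It runs from about 4-6% of truly normal outcomes under the mildest check to 35-40% under the strictest cell-by-cell check, against 4-5% for residuals. These figures assume Shapiro-Wilk at 5%, 10-30 per arm and visit correlation 0.6-0.8. The cost of a diversion, once it happens, is clear: Friedman answers whether values change over time, and its 5% level is not a 5% level for a difference between arms. This should be corrected before analysis.

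**What to change.** For the outcome measures only:

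1. State that the mixed model is the between-group analysis for every outcome, with no normality test deciding its use.
2. State that residuals from the fitted model will be inspected as a diagnostic.
3. Replace the closing Friedman sentence. If residuals are clearly skewed, report the same group contrast with a permutation p-value obtained by re-randomising arm labels within the randomisation blocks, or fit the model on a transformed scale named in advance. The contrast itself should be written down beforehand.

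Leave the normality provisions for the demographic comparisons and for the Pearson or Spearman correlations as they are.

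Cost: a few sentences in the SAP and a short permutation script. No extra data or visits are needed.

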At each follow up visit the log book entries will be collected and reviewed. A second investigator will inspect the residual limb and check the fit of the prosthetic socket, record residual limb knee extension strength on the Biodex machine, take anthropometric measurements (circumferences and lengths) of the residual limb with a tape measure and ruler, and scan the limb with the hand held three-dimensional motion-tracking laser scanner system. The participant will be asked to complete the pain questionnaire at all four followup visits and the Prosthetic Evaluation Questionnaire (PEQ) at the 12 weeks and 3 month followup visits.

For the isokinetic evaluation with the Biodex, the individuals will be positioned in the dynamometer, sitting with the trunk, pelvis and thigh stabilized by belts. The back of the chair will be inclined at an 85 degree angle and the rotational axis of the device will be aligned with the rotational axis of the knee joint, at the level of the lateral epicondyle of the femur. The lever arm was positioned parallel to the leg, with the support cushion modified for the amputee and positioned at the mid-calf. The test will be performed in a total range of motion of 110 degrees. The knees will be positioned in 60 degrees of flexion to start.

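### The planned group-by-time ANOVA does not adjust for the baseline outcome; if baseline is a level of time, the group main effect understates the treatment effect and should not be the treatment test

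*Combined protocol and SAP*

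**What the plan says.** The Statistical Plan section gives the main analysis in one sentence: "A mixed model repeated measures ANOVA will be used to compare the outcome measures between groups and overtime". On covariates it says only: "Compliance with the FES (e.g. average number of hours of use per week) will be entered as a covariate". The tests that lead to further comparisons are introduced by "Should significant main and interaction effect differences be found" (at p < 0.05), after which "post-hoc analyses will be used to examine the differences in variables across the groups and time points". The section does not list the levels of time, say how baseline enters, or name one effect or visit as the treatment test.

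Under Study Design and Methods, the schedule reads: "The study consists of a baseline visit and four follow up visits at 4 weeks, 8 weeks, 12 weeks and one final visit", with the last visit three months after week 12 or after FES is stopped. Participants are "randomized into two groups using a random block method at the end of the baseline visit", so baseline is pre-treatment. The outcomes are measured then: "The following procedures and outcome measures will be obtained from a blinded (second) assessor at the baseline visit", followed by strength, limb volume, pain, PEQ and gait. At follow-up the PEQ is collected less often than the pain questionnaire: "Prosthetic Evaluation Questionnaire (PEQ) at the 12 weeks and 3 month followup visits". Hypothesis 4 compares the groups on change in gait from baseline.

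**The concern.** In a randomised trial with a pre-treatment measurement of the outcome, that measurement is usually among the best predictors of later values. This is plausible for strength, limb volume and gait speed, which differ widely between people. The plan adjusts for something else, FES compliance, which arises after randomisation and is logged only in the FES group, so it cannot stand in for baseline.

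Two things are at stake. First, if baseline is a level of time, the group main effect averages in a visit at which treatment cannot have made a difference, together with a visit about three months off treatment. No hypothesis asks about that average, yet the plan tests it and does not rule it out as the treatment result. Second, group comparisons at single visits, as the post-hoc step is worded, would have larger standard errors than the data require and would stay open to chance imbalance at baseline.

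**Working it through.** **Inputs from the document.** Five visits (baseline, weeks 4, 8, 12 and final); three for the PEQ (baseline, week 12, final); randomisation after the baseline measurements; FES compliance as the only covariate.

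**Inputs that are assumed.** The document gives no sample size, SD, correlation or effect size, so there is no planned figure to reproduce. I take SD = 1 at every visit and the same correlation rho between any two visits, with rho from 0.5 to 0.8 as the main range and 0.3 as a low value.

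**1. Group main effect with baseline as a level of time.** With k post-baseline visits, a constant effect d at each and zero at baseline, the group main effect estimates d × k/(k+1).
- Outcomes with four follow-up visits: 4/5 = 0.80 of d.
- PEQ, two follow-up visits: 2/3 = 0.67 of d.

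These are upper limits if the effect builds up to d or fades from it. For an effect of 1/3, 2/3 and 1 at weeks 4, 8 and 12, with half kept at the final visit, the five-visit mean is (0 + 1/3 + 2/3 + 1 + 1/2)/5 = 0.50 of the week-12 effect. With none kept it is 2/5 = 0.40. Without baseline the same profiles give 2.5/4 = 0.625 and 2/4 = 0.50. Most of the shortfall there comes from the assumed build-up and fade, and only part from including baseline.

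**2. Variance of the group difference at one visit**, in common units:
- unadjusted: 1
- change from baseline: 2(1 − rho)
- baseline-adjusted: 1 − rho²

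Relative to the adjusted comparison, the unadjusted one is 1/(1 − rho²) and the change contrast is 2(1 − rho)/(1 − rho²) = 2/(1 + rho).

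| rho | unadjusted / adjusted | change / adjusted |
|---|---|---|
| 0.3 | 1/0.91 = 1.10 | 2/1.3 = 1.54 |
| 0.5 | 1/0.75 = 1.33 | 2/1.5 = 1.33 |
| 0.7 | 1/0.51 = 1.96 | 2/1.7 = 1.18 |
| 0.8 | 1/0.36 = 2.78 | 2/1.8 = 1.11 |

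A variance ratio is also the ratio of sample sizes for equal precision. The formulas leave out the small cost of estimating the baseline slope.

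**3. Power, for illustration only.** Assume 15 per arm, a week-12 effect of 0.8 SD, the two build-up profiles in step 1, and two-sided 0.05. For the single-visit contrasts the noncentrality is 15 × 0.8²/(2v) = 4.8/v, with v from step 2.

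| Test | rho 0.6 | rho 0.8 |
|---|---|---|
| Group main effect, five visits | 18–25% | 15–21% |
| Omnibus group-by-time interaction (4 df) | 50–65% | 83–93% |
| Week 12, unadjusted | 56% | 56% |
| Week 12, change from baseline | 66% | 92% |
| Week 12, baseline-adjusted | 75% | 94% |

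The ranges cover the two profiles. The adjusted comparison has the highest power in each column. The interaction and the change contrast come much closer to it than the group main effect does, especially at rho 0.8.

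**The case against.** **The plan never says that baseline is a level of time.** That is correct; it is inferred. It is the natural reading, because baseline is not a covariate and an analysis with baseline in neither place could not address the change that Hypothesis 4 describes. If another reading was intended, the text still has to say so.

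**A reader might infer that the plan wastes the baseline data.** The document does not support that. It tests the interaction as well as the main effects. With baseline as a level of time, the interaction compares change between the groups, uses every participant's baseline as reference, is not diluted, and answers Hypothesis 4. Its change contrast loses least when rho is high, which is the case in which baseline matters most. Setting the power of the group main effect against that of the adjusted week-12 comparison, and leaving out the interaction, would exaggerate the cost. What remains is that the omnibus test gives no week-12 estimate, and the post-hoc step that follows it specifies no baseline adjustment.

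**A reader might also infer that baseline as a level of time is an error in itself.** It is not. A model that keeps baseline as a response and constrains its mean to be equal across arms is about as efficient as covariate adjustment. The plan does not state that constraint.

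**Every variance and power figure is assumed.** This stands. The fractions 4/5 and 2/3 need only the visit count and a constant effect; the rest depends on rho, and the power figures also on an invented sample size and effect.

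**Conclusion.** The point holds as one of efficiency and specification. The plan does not adjust for the baseline outcome. On the natural reading, the group main effect estimates at most 4/5 of a constant treatment effect (2/3 for the PEQ) and should not be the treatment test. The interaction is sound for Hypothesis 4, but its single-visit change contrast has 1.33 (rho 0.5) to 1.11 (rho 0.8) times the variance of a baseline-adjusted comparison. Unadjusted visit-wise comparisons have 1.33 to 2.78 times that variance. The ratios assume equal variances and a rho that the document does not give. Randomisation keeps the planned comparisons valid, so this is a change that should be made and not a flaw that invalidates the trial.

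**What to change.** In the Statistical Plan:

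1. State how baseline enters. For each outcome, fit a linear mixed model to the post-baseline visits at which it is collected (weeks 4, 8, 12 and final; week 12 and final for the PEQ), with the participant's baseline value (by visit) as a covariate, plus group, visit and group-by-visit. Alternatively, keep baseline as a response with its mean constrained equal across arms.
2. Report the FES-minus-control difference at week 12 with its 95% CI as the training effect, and the difference at the final visit as the carry-over effect.
3. State that the group main effect over all visits is not the treatment test.

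Baseline is already collected, so no new data or visits are needed. The cost is wording, and one degree of freedom for the adjustment, or a few if baseline interacts with visit.

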Muscle performance will be evaluated at angular velocity of 60, during isokinetic quadriceps contractions. To assure familiarization with the procedures the participant will have two practice submaximal trial repetitions set at the velocity of 60 and one practice trial. The test will consist of 5 repetitions at 60/s. There will be a 60 second interval between repetitions tested. During evaluation, the participants will be verbally instructed to move the lever of the dynamometer as fast and as powerfully as possible, trying to produce a maximum torque. Any complaints reported by the participant will be recorded in the comment section and, if necessary, the test will be stopped. Using the same seat set up, muscle performance will be evaluated during static concentric (isometric) quadriceps extension contractions. The lever arm will be positioned at 60 degrees of knee flexion, with the support cushion modified for the amputee and positioned at mid calf. The participant will have one practice submaximal trial contraction. The test will consist of three contractions for five seconds each. There will be a 60 second interval between each test. During evaluation, the participants will be verbally instructed to move the lever of the dynamometer as powerfully as possible, trying to produce a maximum torque. Any complaints reported by the participant will be recorded in the comment section and, if necessary, the test will be stopped.

At the 12 week visit, the intervention group participants will return the FES device. They will be followed up with one final visit 3 months after the FES device is returned.

At the end of the study, should the study find the FES intervention is beneficial, we will offer the control group the same intervention. It will be optional per participant request.

If a subject misses the last visit or is dropped from the study for a reason not related to the study and or beyond our control, we will ask to set up a follow up visit, face to face, or a phone interview to allow us to gather end result information and complete the data analysis.

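### No primary outcome, deciding effect or definition of benefit: at least seven hypothesised endpoints are tested at an unadjusted 0.05, so the main question has no controlled error rate

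*Combined protocol and SAP*

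**What the plan says.** The Statistical Plan gives one analysis for everything measured: "A mixed model repeated measures ANOVA will be used to compare the outcome measures between groups and overtime". The only significance threshold appears in the sentence "Should significant main and interaction effect differences be found ( $p < 0.05$ ), post-hoc analyses will be used". No adjustment, ordering of outcomes or deciding visit is given, and the post-hoc method is not specified.

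The Objective (under Background) asks one broad question, whether home FES brings benefits. Four hypotheses follow, on knee extension strength, limb volume, chronic and phantom pain, and three gait measures. The nearest thing to a primary outcome is the Background remark that "one of the main functional outcomes that we are investigating is knee extension".

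Study Design and Methods adds measurements. Strength is tested twice: "Muscle performance will be evaluated at angular velocity of 60, during isokinetic quadriceps contractions", and then, in the same seat set-up, "muscle performance will be evaluated during static concentric (isometric) quadriceps extension contractions". Assessors also "take anthropometric measurements (circumferences and lengths) of the residual limb with a tape measure and ruler", and participants complete the PEQ. The same section attaches an action to the result: "should the study find the FES intervention is beneficial, we will offer the control group the same intervention". It does not say which outcome, visit or model effect would establish benefit.

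**The concern.** When many outcomes are each tested at 0.05 and none is designated to decide, one nominal hit can be presented as the answer to the Objective, and the chance of such a hit when the device does nothing is well above that of a single test. The plan also leaves open which effect counts. A repeated-measures ANOVA over five visits yields a group effect, a time effect and a group-by-time interaction, and the plan does not choose among them. Only Hypothesis 4 mentions the control group, so a change over time alone might be offered as support for Hypotheses 1 to 3.

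At stake is the credibility of any statement that FES works, and the decision to offer it to controls.

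**Working it through.** The documents state no family-wise error rate, power or sample size, so there is no figure of the plan's own to reproduce.

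**Counting endpoints**
- Hypotheses: strength 1 + volume 1 ("Hypothesis 2: FES will increase volume of the residual limb") + chronic and phantom pain 2 + velocity, step length and percent stance time 3 = 7.
- Isokinetic and isometric strength analysed separately: 7 + 1 = 8.
- PEQ taken as one score, plus circumferences and lengths: 8 + 1 + 2 = 11.

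**Inputs**
- Significance level 0.05 per test (Statistical Plan). Sidedness is not stated. An ANOVA F test ignores direction, so I treat it as two-sided, with 0.025 in the favourable direction.
- Assumed: one between-group test per outcome, no true effect on any outcome, and any one hit counts.
- Correlation between outcomes is not given, so I show a range.

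**Independent outcomes**
- Either direction: 1 − 0.95^k. Favouring FES: 1 − 0.975^k.
- k = 7: 30.2% and 16.2%.
- k = 8: 33.7% and 18.3%.
- k = 11: 43.1% and 24.3%.

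**Correlated outcomes, k = 8.** Each test statistic is √r·W + √(1−r)·e_j, where W is a standard normal shared by all outcomes and e_j is a standard normal specific to outcome j. There were 300,000 draws.

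| Correlation r | Any significant difference | One favouring FES |
|---|---|---|
| 0 (formula above) | 33.7% | 18.3% |
| 0.3 | 30.0% | 15.1% |
| 0.5 | 24.9% | 12.5% |
| 0.6 | 22.0% | 11.0% |
| 0.8 | 15.7% | 7.8% |

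**Comparator.** One two-sided 0.05 test gives 2.5% in the favourable direction. The ratios are 18.3/2.5 = 7.3, 12.5/2.5 = 5.0 and, at r = 0.8, 7.8/2.5 = 3.1.

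**Check on the planned model.** I simulated the repeated-measures ANOVA under no effect, with 8 outcomes, 5 visits, 10 or 20 per arm, within-person correlation 0.6, between-outcome correlation 0 to 0.5, and 4,000 runs per setting. Arm sizes and correlations are assumptions. Direction for the interaction was read from the between-arm difference in change from baseline to week 12.
- Interaction only: about 26-34% for any hit and 14-19% for a favourable one, in line with the table.
- Group effect or interaction counted, so 8 × 2 = 16 tests: about 44-56% for any hit and 24-33% for a favourable one.
- Both required on the same outcome, treated as independent: 0.05 × 0.05 = 0.0025 per outcome, and 1 − (1 − 0.0025)^8 = about 2%, in either direction.

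**The case against.** The strongest reply is that the plan contains no rule under which one hit means success. In the Statistical Plan, p < 0.05 only triggers post-hoc analyses, and the four hypotheses can be reported separately. That stands: the figures above describe one way the results might be read, not a procedure the plan prescribes.

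A reader might go further and infer that an ineffective device has a 25-34% chance of being declared beneficial. The documents do not support that. The range counts differences in either direction, and false harm is as likely as false benefit. On the one-test-per-outcome basis the favourable share is about 12-18%. A favourable figure of 24-33% needs both the group effect and the interaction to count as routes to benefit, which the plan neither states nor excludes. Its wording joins main and interaction effects with 'and'; if both were required, the figure would drop to about 2%. A spread from about 2% to more than 50% across readings of one sentence shows that the deciding effect needs to be named.

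Correlation is also a fair point. The two strength tests use the same muscle, and the gait measures come from the same walks, so some pairs may correlate above 0.5. Even at 0.8 throughout, the favourable figure is about three times that of one test.

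The consequence for controls is modest, since taking up the offer is optional. And the study may have been meant as exploratory, but the documents do not say so. They state directional hypotheses and plan an action if benefit is found.

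**Conclusion.** The point holds as a missing decision rule with a material effect on error. At least seven hypothesised endpoints (eight with both strength tests) are tested at an unadjusted 0.05, with no primary outcome, deciding visit, deciding model effect or definition of benefit. If any one nominal group difference were taken as success, an ineffective device would show at least one in about 25-34% of trials, and one favouring FES in about 12-18%, against 2.5% for a single test. This rests on eight outcomes, one test per outcome and assumed correlation from 0.5 down to 0. At correlation 0.8 the figures are about 16% and 8%. That one hit would suffice is an assumption; that the plan does not rule it out is a matter of record.

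**What to change.** Before analysis:

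1. Name one primary test: for example, the between-arm difference in change from baseline to week 12 in one pre-chosen Biodex knee extension measure, at two-sided 0.05. This fits Hypothesis 1 and the visit at which the device is returned. The sponsor may justify another primary, such as pain, since chronic limb pain is an entry criterion.
2. Base any statement that FES is beneficial on that test.
3. Test the secondary endpoints only if the primary is significant, with Holm across all six individually: volume, chronic pain, phantom pain, velocity, step length and percent stance time. The first Holm step is 0.05/6 = 0.0083. Making this conditional matters: Holm at 0.05 run regardless of the primary would allow up to 0.05 + 0.05 = about 10% family-wise error. Listing six endpoints rather than three hypotheses also covers multiplicity within pain and within gait.
4. Report the other strength measure, circumferences, lengths, PEQ and the correlations with amount of FES used as exploratory.

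Label: cheap improvement. It needs wording in the Statistical Plan and a matching line in the Objective, and uses data already to be collected. The downside is that secondary p-values become less favourable and confirmatory claims are limited if the primary fails. Power for the chosen primary cannot be judged here, because the documents give no sample size.
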